#### 8.1.3 Visit 2: Surgery

*[Purpose: To collect data on the performance of intra-operative molecular imaging]*

1. AEs and ADEs will be recorded during and following surgery.

03 Sep 2025

2. After the surgical site is visualized under normal light and/or palpation, the number and location of suspect lesions detected under normal light will be recorded on the schematic using an “O”.
3. Following the assessment by normal light, subjects will undergo fluorescence imaging of the surgical field. Suspect lesions detected under fluorescence imaging will be marked on the schematic using an “X”.
4. All identified suspect lesions will be marked on the schematic (“O”, “X”, or “⊗” as described in [Section 4.1.3](#)) and excised, at the discretion of the Investigator.
5. Sentinel lymph node biopsy will be performed at the Investigator’s discretion per the standard of care.
6. All excised lesions will be sent to the local laboratory for histopathology and immunohistochemistry staining. A unique identifier will be assigned to each excised lesion and the location of each will be recorded along with the unique identifier. If an organ/large section of tissue (e.g. uterus, omentum) with multiple lesions is excised *in toto*, one grossly positive lesion will be utilized for the purposes of calculating sensitivity and FR expression.
7. Histopathology, folate receptor expression, and genomic testing results will be recorded once data is received per institutional practices and timeline.

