### **8.3.3     *Unanticipated Adverse Device Effect (UADE)***

#### Risk of Misinterpretation

Errors may occur with the use of OTL38 during intraoperative fluorescence imaging to detect ovarian cancer and lesions in the lung, including false negatives and false positives. Non-fluorescing tissue in the surgical field does not rule out the presence of ovarian cancer or lesions in the lung. Fluorescence may be seen in normal tissues including bowel, kidneys, lymph nodes, and lungs as well as in inflamed tissues.

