## 9 STATISTICAL CONSIDERATIONS

### 9.1 Statistical Hypotheses

- Primary Efficacy Endpoint:
  - The primary efficacy endpoint is the sensitivity of CYTALUX with NIR imaging for detection of malignant lesions. Sensitivity is defined as the proportion of fluorescent light positive lesions that are histologically confirmed to be cancer relative to the total number of lesions confirmed to be cancer.  
Sensitivity = (True Positive)/(True Positive + False Negative)
- Secondary Efficacy Endpoints:
  1. Incidence rates of all adverse events (AEs), adverse device effects(ADEs), and SAEs, from the time of CYTALUX administration through Visit 3
  2. Sensitivity for cancerous lesions for:
    - a. FR $\alpha$  positive lesions
    - b. FR $\beta$  positive lesions
- Exploratory Endpoints:
  1. Genomic evaluation of tumor inclusive of, but not limited to:
    - a. Estrogen receptor/progesterone receptor (ER/PR) status
    - b. HER2 status
    - c. Mismatch repair (MMR) status
    - d. POLE status
    - e. p53 status
    - f. CARIS whole genome sequencing
  2. The exploratory endpoint is the detection rate of CYTALUX with NIR imaging for identification of SLNs. The detection rate is the proportion of the patients with SLNs detected by CYTALUX and NIR imaging in all enrolled patients.

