### **9.2.2 Analysis of the Primary Efficacy Endpoint**

The primary analysis of the primary endpoint will include subjects exposed to CYTALUX™ (pafolacianine) injection and undergo fluorescent imaging (CYTALUX™ (pafolacianine) injection+Imaging) who:

- Received study drug and were evaluated under NIR fluorescent light imaging during surgery

The primary analysis of the efficacy endpoint will be a one-sample test for a proportion via an exact binomial test conducted at the two-tailed alpha level of 0.05. The test will compare the observed proportion against a threshold of 0.10. The efficacy of CYTALUX™ (pafolacianine) injection in combination with fluorescent imaging will be confirmed if the null hypothesis is rejected and the observed proportion is greater than 0.10. The two-sided 95% confidence interval (CI) will also be calculated.

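### Efficacy is declared confirmed on lesion sensitivity above 0.10 alone, and no endpoint uses false positives, although the protocol warns of them

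*Protocol*

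**What the plan says.** The primary endpoint (protocol synopsis, section 3 and section 9.1) is lesion-level sensitivity, TP/(TP+FN), with histology as reference. Section 9.2.2 tests it with an "exact binomial test conducted at the two-tailed alpha level of 0.05" and adds: "The test will compare the observed proportion against a threshold of 0.10". Efficacy of the agent with fluorescent imaging "will be confirmed if the null hypothesis is rejected and the observed proportion is greater than 0.10". No other condition is attached.

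The only other lesion-performance endpoint is again "Sensitivity for cancerous lesions for" folate-receptor alpha and beta positive lesions. The exploratory endpoints are genomic markers and the proportion of patients in whom sentinel nodes are detected. Specificity, PPV, a false-positive rate and a false-positive count appear in no endpoint list or analysis.

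Section 8.3.3 lists errors of interpretation, "including false negatives and false positives", and states: "Fluorescence may be seen in normal tissues including bowel, kidneys, lymph nodes, and lungs as well as in inflamed tissues".

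The raw material for a false-positive measure is collected. Under 4.1.3, tissue removed as standard of care is imaged under near-infrared light before and after resection and compared with pathology. Lesions seen only under fluorescence are marked X. Section 8.1.3 adds: "All excised lesions will be sent to the local laboratory for histopathology", with a unique identifier for each lesion.

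**The concern.** The primary objective is detection of malignant tissue. Sensitivity describes what happens in malignant lesions only, and cannot show that the agent separates malignant from benign tissue. That would be acceptable if the result were reported simply as sensitivity. Here the protocol fixes in advance that passing the test confirms efficacy.

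The risk left out of the rule is one that the protocol names. Bowel segments and lymph nodes, both listed in 8.3.3, also appear on this study's surgical schematic (Appendix 1). Section 2.3 describes surgeons using fluorescence when deciding what to remove, and 8.1.3 allows fluorescence-only suspects to be excised at the investigator's discretion. A false positive can therefore mean that benign tissue is removed, and no endpoint records it. The sentinel-node detection rate does not help, because it counts patients with a detected node whether or not the node is malignant.

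**Working it through.** **Inputs from the protocol.** Endpoint TP/(TP+FN) (9.1). Null value 0.10, exact binomial, two-sided 0.05, and success if the null is rejected with the observed proportion above 0.10 (9.2.2). Enrolment of 10 subjects (synopsis). The protocol gives no power, assumed sensitivity or lesion count, so there is no planned figure to reproduce.

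**Assumptions.** The number n of histologically malignant lesions is not stated, so a range is shown. Lesions are treated as independent, as the planned test treats them. A non-discriminating agent is modelled as one that fluoresces in any tissue, malignant or benign, with the same probability q. Its sensitivity is q and its false-positive rate is also q.

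**Step 1: an agent that lights everything (q = 1).** FN = 0, so observed sensitivity is 1.00 and p = 0.10^n. For n = 1, p = 0.10 and the test cannot reject. For n = 2, p = 0.01. For n = 10, p = 1e-10. The rule is met with certainty from two malignant lesions upward, at specificity 0.

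**Step 2: the critical count.** Rejection is taken as an upper tail of at most 0.025 under 0.10. At n = 10, P(X ≥ 3) = 0.0702 fails and P(X ≥ 4) = 0.0128 passes, so four fluorescent cancers suffice.

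**Step 3: probability that a non-discriminating agent meets the rule**, P(X ≥ r) with X binomial(n, q):

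| Assumed n | Needed r | Upper tail at 0.10 | q = 0.3 | q = 0.5 | q = 1 |
|---|---|---|---|---|---|
| 2 | 2 | 0.0100 | 0.090 | 0.250 | 1 |
| 5 | 3 | 0.0086 | 0.163 | 0.500 | 1 |
| 10 | 4 | 0.0128 | 0.350 | 0.828 | 1 |
| 20 | 6 | 0.0113 | 0.584 | 0.979 | 1 |
| 30 | 8 | 0.0078 | 0.719 | 0.997 | 1 |

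A hand check at n = 10, q = 0.5: 1 − (1 + 10 + 45 + 120)/1024 = 1 − 176/1024 = 0.828. The other common two-sided exact definition gives the same or a one-lower cut-off (5 instead of 6 at n = 20), so it is never harder to pass.

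**Step 4: the rule does not react to false positives.** Suppose 16 of 20 cancers fluoresce (assumed counts). Sensitivity is 0.80, exact 95% CI 0.56 to 0.94, and the rule is met. With 0 benign fluorescent lesions PPV is 16/16 = 100%. With 20 it is 16/36 = 44%. The stated conclusion is the same in both cases.

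**Step 5: which measure would expose the fault.** For an agent that lights everything, PPV equals the malignant share of the excised lesions. With an assumed 20 malignant and 5 benign, PPV is 20/25 = 80% although the agent discriminates nothing. The false-positive rate FP/(FP+TN) in the same data is 5/5 = 100%. PPV alone can hide the problem, whereas the fluorescence rate in benign specimens shows it. The share of fluorescent lesions that are benign is 1 − PPV, so it adds nothing to PPV.

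**The case against.** This is a single-arm, open-label pilot in 10 patients, and sensitivity directly answers whether malignant tissue is detected. The endpoint is defined consistently throughout. Descriptive false-positive tables are often left to the statistical analysis plan, which is not shown. Section 4.1.3 already foresees comparing near-infrared findings with pathology for all tissue removed as standard of care, benign tissue included.

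Much of this stands. A sensitivity endpoint in a pilot is not a fault, and the absence of a table from the protocol would not be one by itself. But the rule that efficacy is confirmed is fixed in the protocol, and a table in an unseen plan would not remove it. The comparison in 4.1.3 names no statistic and does not enter the rule.

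Three stronger readings are tempting, and the documents do not support them:

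- A reader might infer that the protocol expects false positives in this trial. Section 8.3.3 says only that they may occur, in text written about ovarian and lung use. It is a warning and gives no rate.
- A reader might infer that removal of benign tissue is the main cost to patients. The risk section (2.4.1) does not list unnecessary resection. Sections 2.3 and 8.1.3 make such a cost possible, but nothing ranks it.
- A reader might infer that the agent discriminates poorly. The calculations describe what the rule would accept and say nothing about how the agent behaves.

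**Conclusion.** The concern holds as a fault in the conclusion that 9.2.2 permits. The choice of sensitivity as primary endpoint can stay. Meeting the rule shows that more than 10% of malignant lesions fluoresce; it does not show that fluorescence distinguishes malignant from benign tissue. Non-discriminating agents pass easily: with certainty at q = 1 from two malignant lesions, a number that 10 patients with endometrial cancer will very probably supply, and with probability about 0.83 to 0.98 at q = 0.5 for 10 to 20 lesions. The low threshold makes this worse, since at q = 0.3 the probability is still 0.35 to 0.58.

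These figures rest on assumed lesion counts and on independence between lesions. Step 1 needs no lesion count beyond two. The change is worth making before data are seen, since the study is open-label and a false-positive measure chosen afterwards could be selected for its result.

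**What to change.** 1. In 9.2.2, replace the statement that efficacy is confirmed with a conclusion limited to what is tested. For example: *rejection in the upward direction supports the conclusion that lesion sensitivity exceeds 0.10; this is to be read together with the false-positive results.*
2. Add a descriptive secondary endpoint in section 3, 9.1 and the synopsis:
   - false-positive rate: histologically benign resected specimens that fluoresced, divided by all histologically benign resected specimens imaged;
   - PPV among excised fluorescent lesions, TP/(TP+FP);
   - results for fluorescence-only (X) lesions shown separately;
   - counts per patient, and 95% confidence intervals that allow for clustering within patient, labelled approximate with 10 patients.
3. State the limits. Both measures cover excised tissue only, because excision of suspect lesions is at the investigator's discretion (8.1.3). The rule in 8.1.3 that an organ removed whole with several lesions contributes one grossly positive lesion affects the counts, so the protocol should say how benign areas of such an organ are counted.

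Cost: wording in four places and one more table. The near-infrared assessment, lesion marks, identifiers and histology are already planned, so no new data are needed and no clinical procedure changes. The downside is that a less favourable and imprecise number may stand beside the primary result.

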### **9.2.3 Safety Analyses**

Safety will be described via subject incidence of treatment emergent adverse events (TEAEs) including serious TEAEs as well as adverse device effects (ADEs) considered as causally related.

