### 1.3 Schedule of Activities (SoA)

Study Procedure	Screening Visit	Visit 1	Visit 2	Visit 3
	-30 days prior to surgery	-7 days to day of surgery	Day of surgery	4 weeks ±1 week post-surgery
Informed consent	X			
Medical history	X			
Confirmed surgical candidate	X			
Pregnancy test for patients of childbearing potential		X		
Study drug administration		X		
Surgery with associated procedures including intraoperative imaging and sentinel lymph node biopsy			X	
Histopathology assessment of resected tissue*			X	
Collection of genomic marker data**			X	
AE assessments		X	X	X
ADE assessments			X	X

\*Lesions will be resected during the surgery at Visit 2. Histopathology assessment and immunohistochemistry staining will be completed in accordance with local pathology procedures and timeline.

\*\*Genomic marker data obtained prior to surgery will be utilized, if available. If tissue is collected during surgery for genomic testing, the testing will be completed in accordance with institutional procedures and timeline.

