## 2.4 Risk/Benefit Assessment

### 2.4.1 Known Potential Risks

The safety of CYTALUX was evaluated in four open label clinical studies, two studies (N = 44 and N = 150) in patients with ovarian cancer and two studies (N = 100 and N = 112) in patients with known or suspected cancer in the lung. A total of 406 patients received 0.025 mg/kg of CYTALUX via intravenous administration. Adverse reactions that occurred in  $\geq 1\%$  of patients were: nausea (13%), vomiting (5%), abdominal pain (2%), flushing (2%), other infusion-related reactions (2%), hypersensitivity (2%), elevation in blood pressure (1%), dyspepsia (1%), and chest discomfort (1%). Adverse reactions occurred during the administration of CYTALUX in 17% of patients. During the administration of PAFOLACIANINE, interruption of the infusion and/or treatment with an anti-histamine may be required in subjects who experience symptoms suggestive of hypersensitivity, followed by an observational period until the symptoms resolve. Anti-nausea (e.g. Zofran) and anti-histamine (e.g. benadryl) are frequently dosed prior to infusion of Pafolacianine in clinical practice to limit side effects. Symptoms to be aware of may include but are not limited to flushing, nausea, vomiting, abdominal pain and pruritis/urticaria. Other risks to subjects may include injection site adverse reactions (infusion and venous blood sampling), such as infection and hematoma. The use of a near-infrared fluorescence camera system during surgery may result in contamination of the sterile field or injury due to disengagement of the imaging device component coming in contact with the patient and/or surgical team. No clinically meaningful changes in vital signs, laboratory parameters, or electrocardiograms have been observed. Adverse events in the prior studies have been attributable to the underlying disease or to surgery (most commonly lymphedema, post-procedural hematoma, or urinary incontinence). Overall, the administered doses of PAFOLACIANINE have been well tolerated. The time spent visualizing the surgical field under NIR is quite short, with no meaningful prolongation of anesthesia. There are no known hazards associated with exposure of tissue to near-infrared light for short periods of time.

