### 3 OBJECTIVES AND ENDPOINTS

OBJECTIVES	ENDPOINTS
Primary	
To assess the ability of CYTALUX™ (pafolacianine) injection used with near-infrared (NIR) fluorescent imaging for the detection of malignant tissue in subjects undergoing surgical resection for endometrial cancer	
Sensitivity is defined as the proportion of fluorescent light positive lesions that are histologically confirmed to be cancer relative to the total number of lesions confirmed to be cancer.
 
Sensitivity = (True Positive)/(True Positive + False Negative)

Secondary	

 
1. To assess the safety of CYTALUX in subjects undergoing surgery for endometrial cancer
 
2. To assess folate receptor (alpha and beta expression) in resected specimens
 
	
 
1. Incidence rates of all adverse events (AEs), adverse device effects (ADEs), and SAEs, from the time of CYTALUX administration through Visit 3
 
2. Sensitivity for cancerous lesions for: 
 
a. FR<math>\alpha</math> positive lesions
 
b. FR<math>\beta</math> positive lesions
 
 
 

Exploratory	

 
1. To assess the feasibility of using genomic markers to predict utility of CYTALUX with NIR imaging
 
2. To assess the feasibility of CYTALUX to identify sentinel lymph nodes
 
	
 
1. Genomic evaluation of tumor inclusive of, but not limited to: 
 
a. Estrogen receptor/progesterone receptor (ER/PR) status
 
b. HER2 status
 
c. Mismatch repair (MMR) status
 
d. POLE status
 
e. p53 status
 
f. CARIS whole genome sequencing
 
 
 
2. The exploratory endpoint is the detection rate of CYTALUX with NIR imaging for identification of sentinel lymph nodes (SLNs). The detection rate is the proportion of the patients with SLNs detected by CYTALUX and NIR imaging in all enrolled patients.
 

03 Sep 2025

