#### 8.1.2 Visit 1: Infusion

*[Purpose: To infuse CYTALUX™ (PAFOLACIANINE) INJECTION]*

1. Patients with a known allergy to CYTALUX (pafolacianine) will be given pre-medication of 25 mg Benadryl and 4 mg Zofran as prophylaxis approximately 30 minutes prior to the start of infusion, unless a patient has a history of allergy to either drug.
2. A single dose of CYTALUX will be infused IV over 60 minutes
3. AEs will be recorded during infusion of CYTALUX.

Should the patient experience suspected adverse events during infusion, the infusion will be stopped, and the Principal Investigator (PI) will be contacted for discussion and assessment. Per PI discretion, the patient will be treated for symptoms and infusion can be started again to assess for tolerance. If infusion is still not tolerated, amount infused will be recorded and imaging portion of study will proceed.

4. Intraoperative imaging should begin within 1 to 168 hours (7 days) after the completion of infusion.

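### The safety endpoint counts all adverse events in one window spanning surgery, Section 8.3.1 records only related ones, and Section 9.2.3 neither settles the scope nor separates the infusion from the operation

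*Protocol*

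**What the plan says.** Secondary objective 1 is the safety of CYTALUX. The matching endpoint (Synopsis, Section 3 and Section 9.1) is the incidence of all adverse events, adverse device effects and "SAEs, from the time of CYTALUX administration through Visit 3". The Schedule of Activities places Visit 3 at "4 weeks ±1 week post-surgery".

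The analysis in Section 9.2.3 reads "Safety will be described via subject incidence of treatment emergent adverse events (TEAEs"); it goes on to name serious TEAEs and device effects, followed by a qualifier about causal relation. It gives no time periods.

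Data collection is described differently in different places:

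- Section 8.1.2: "AEs will be recorded during infusion of CYTALUX".
- Section 8.1.3: "AEs and ADEs will be recorded during and following surgery".
- Section 8.3.1 limits documentation to events and device effects judged causally related to the product.
- Section 8.3.2 has every serious event documented, whatever its cause.
- Section 8.3.4.2 has each event graded Related or Not Related from its timing and clinical judgment.

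On the known profile of the agent, Section 2.4.1 lists nausea (13%), vomiting (5%) and abdominal pain (2%) among 406 patients and adds: "Adverse reactions occurred during the administration of CYTALUX in 17% of patients".

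**The concern.** The study has one arm, 10 patients and no blinding, and imaging at surgery follows the end of infusion by 1 to 168 hours. The window fixed for a drug-safety endpoint is therefore taken up largely by an operation and the recovery from it. The agent's commonest reactions (nausea, vomiting, abdominal pain) are also things that surgery and anaesthesia can cause.

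Two questions decide what the reported incidence will mean: which events enter it, and whether events before the operation are shown apart from those after it. The protocol answers the first inconsistently and does not address the second, although the visit procedures already record infusion and surgical events in separate steps. What is at stake is whether the result of secondary objective 1 can be read as a statement about the drug.

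**Working it through.** The protocol gives no power or precision figure for safety, so there is nothing of its own to reproduce. The check sets the rules side by side and then illustrates what each would produce.

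**Scope of the events**

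| Place | Which events |
|---|---|
| Synopsis, Sections 3 and 9.1 | all AEs, ADEs and SAEs, dosing to Visit 3 |
| Section 8.3.1 | only AEs and ADEs judged related |
| Section 8.3.2 | all SAEs, no causality filter |
| Section 9.2.3 | TEAEs, serious TEAEs and ADEs; the causality qualifier may attach to all three or to ADEs only |

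The first two rows cannot both hold. An endpoint of all events cannot be computed from records that keep only related ones.

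**If all events count**

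Let d be the drug rate and q the post-operative rate. If they are independent, pooled subject incidence = 1 − (1 − d)(1 − q). The documents give d. They give no q, so q is an assumption and is varied.

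Nausea, d = 0.13 (Section 2.4.1):

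- q = 0.20: 1 − 0.87 × 0.80 = 0.304
- q = 0.30: 1 − 0.87 × 0.70 = 0.391
- q = 0.50: 1 − 0.87 × 0.50 = 0.565

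In 10 patients that is 3.0, 3.9 and 5.7 expected with nausea, of whom 10 × 0.13 = 1.3 have drug nausea.

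Any event, d = 0.17 (reactions during administration, Section 2.4.1):

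| Assumed q | Pooled, 1 − 0.83(1 − q) | Added by the infusion, 0.17(1 − q) |
|---|---|---|
| 10% | 25.3% | 15.3 points |
| 30% | 41.9% | 11.9 points |
| 50% | 58.5% | 8.5 points |
| 70% | 75.1% | 5.1 points |
| 90% | 91.7% | 1.7 points |

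The more common post-operative events are, the less of the drug's contribution shows in the pooled figure.

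**If only related events count**

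Let r be the assumed proportion of patients with another event judged related. Then pooled = 1 − 0.83(1 − r), which is 17.0% at r = 0 and 25.3% at r = 10%. The figure stays near the drug rate, provided the judgment is right.

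That judgment has two levels and is open-label. Under Section 8.3.4.2, Related requires other influences to be unlikely, and Not Related requires a definite other cause to be documented. Nausea a few hours after both infusion and anaesthesia fits neither well. Under Section 8.3.1 a non-serious event judged surgical would not enter the trial data, so the call could not be reviewed from them.

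**Precision at n = 10**

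- At 17%: expected 10 × 0.17 = 1.7 patients; P(at least one) = 1 − 0.83^10 = 84.5%.
- Exact 95% CI (Clopper-Pearson): 1/10 gives 0.3% to 44.5%; 2/10 gives 2.5% to 55.6%.

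**The case against.** A reader might infer that drug reactions cannot be told from post-operative events at all, and that the pooled incidence measures mostly the operation. The documents do not support that. Each event is graded for relatedness partly on timing, Section 8.3.1 would keep unrelated non-serious events out of the count, and recording at infusion is separate from recording at surgery. Section 9.2.3 also names TEAEs, serious TEAEs and ADEs, so it is not literally one number. These points stand, and they confine the masking to the reading in which all events count.

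A reader might also infer that counting events before surgery would recover the 13% nausea rate directly. Section 2.4.1 ties only the 17% to administration. It does not say when the nausea occurred. Its figures are for adverse reactions, so events judged related may be the closer comparator.

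It can further be said that tables by period belong in a statistical analysis plan, which may exist but is not shown. That is fair for the table layout. It does not cover the conflict between Sections 3 and 9.1 and Section 8.3.1, which is in the protocol itself, and no analysis plan can tabulate events that were never documented.

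Finally, the split is imperfect. The first period varies from hours to about 7 days, so a late drug reaction in a patient dosed on the day of surgery may fall into the second. This stands as a limitation.

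**Conclusion.** The concern holds in a limited form. The protocol contradicts itself on which adverse events the safety endpoint contains, and neither reading gives a well-founded drug-safety result as planned. With all events, the pooled figure can hide the drug's contribution: 30% to 57% pooled nausea against 13% from the drug, assuming independence and post-operative nausea of 20% to 50%, neither of which the documents supply. With related events only, the figure is as good as an unblinded judgment that the trial data cannot check.

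Onset period is a more objective separator, and the recording steps come close to supporting it already. It helps only if unrelated events are in fact recorded, so the scope must be reconciled first. The benefit is a summary that can be interpreted. At 10 patients no version permits a precise comparison with 13% or 17%.

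**What to change.** 1. Reconcile the endpoint (Synopsis, Sections 3 and 9.1) with Sections 8.3.1 and 9.2.3, so that all adverse events from dosing to Visit 3 are recorded, each with onset time and relatedness. State in 9.2.3 whether the causality qualifier applies to TEAEs or only to ADEs.
2. In 9.2.3, report subject incidence of TEAEs and serious TEAEs by onset period, (a) start of infusion to start of anaesthesia and (b) start of anaesthesia to Visit 3, and by relatedness. Keep the pooled total.
3. Give the length of period (a) for each patient, and note that a late reaction after same-day dosing may be counted in (b).

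The cost is an onset-time field on the adverse event form, one further split in the safety table, and the recording of unrelated events that Section 8.3.1 now omits. Infusion date and time are already recorded under Section 6.4. The change to collection has to be made before enrolment.
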